3 STUDY SETTING

This is a randomized, controlled clinical trial. The study aims to recruit 40 men on ADT for prostate cancer. This will be a pilot study to estimate effect sizes in Finnish population to inform further larger trial. For this reason the sample size will be smaller compared to previous studies on the topic (10,11) and no power calculation is performed yet.

Figure: Study flow chart

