5 INTERVENTION

All participants attend introductory lecture, where a urologist informs them about adverse effects of ADT and positive effects of exercise during ADT, exercise instructor gives advice for training both at home and in the gym and nutritional therapist tells about nutrition to overcome adverse effects of ADT and support training.

After the introductory lecture the participants are randomized 1:1 to either the supervised or non-supervised exercise group (Figure). Men in the supervised group participate in progressive group exercise sessions twice a week for total of 12 weeks at the Varala sports academy in Tampere, Finland. Each exercise session includes both aerobic and resistance training targeting all major muscle groups (Additional document I, exercise program). The non-supervised group will exercise independently for 12 weeks according to the instructions given at the introductory lecture. The first control visit will be after this first period of 12 weeks of exercise.

After the first follow-up visit both groups will continue non-supervised exercise for 12 weeks, after which the second control visit will be arranged. Special focus on the second control visit is to see how many in each group has been able to carry on active exercising, i.e. has the intervention promoted long-term change in exercise activity.

Both study groups will be given Polar wrist activity monitors to be used 24 h/day for the entire course of the study.

All participants are asked to fill validated quality of life surveys EORTC QLQC-30 (overall quality of life) and EORTC QLQC-PR25 (prostate cancer-specific quality of life) at baseline and again at 1st and 2nd control visits. Plasma lipid and glucose parameters, blood pressure and body composition will be measured at each of these visits.

At each visit a separate blood sample is taken and stored for future measurement of biomarkers associated with prostate cancer progression, glucose and lipid metabolism and effects of exercise.

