7 STUDY OUTCOMES AND STATISTICAL ANALYSIS

Primary outcomes:

- Daily total activity, measured during the entire course of study with wrist activity monitor in metabolic equivalents of task (MET) units
- Fasting plasma cholesterol, LDL, HDL and triglycerides, measured at baseline and again at the 1st and 2nd control visits
- Fasting plasma glucose and glycated haemoglobin (HbA1C), measured at baseline and again at the 1st and 2nd control visits
- Overall quality of life and prostate cancer-specific quality of life, measured with validated Finnish versions of EORTC QLQ-C30 v.3.0 ja EORTC QLQ-PR25 at baseline and at each control visit

Secondary outcomes:

- Change in daily activity after the end of supervised group exercise intervention; difference compared to the non-supervised group. Measured with wrist activity monitor in MET units
- Body mass composition, bioimpedance-based measurement of lean body mass, fat mass and skeletal mass as percentage of total body mass measured with TANITA MC-780 device

- Blood pressure level, measured at baseline and each control visit
- Subjective effect of exercise on quality of life and perceived adverse effects of ADT, as based on qualitative interviews

Long-term follow-up

The participants are followed via patient files and national health care registries. Outcomes to be followed are:

- Time from baseline to castration resistance (progression of prostate cancer despite ADT as evidenced by constantly rising PSA or radiological disease progression)
- Bone fractures
- Diagnosis of memory impairment
- Diagnosis of diabetes mellitus
- Diagnosis of cardiovascular disease
- Prostate cancer death
- Death due to any cause

Statistical analysis

All comparisons are done between the supervised and non-supervised exercise arms. Medians of daily activity (in MET units) and quantitative quality of life (as points from the EORTC surveys) at baseline and at each control visit are compared with either Mann-Whitney U-test or Student's t-test depending on normality of the data distribution. Difference in medians of plasma lipid parameters and glucose parameters are analyzed similarly.

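### Separate unadjusted tests at each visit use only men with a value there, so arm-related, outcome-related drop-out could bias week 24; one baseline-adjusted mixed model per outcome is better

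*Combined protocol and SAP*

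**What the plan says.** Section 7 (Statistical analysis) opens with "All comparisons are done between the supervised and non-supervised exercise arms". Activity and EORTC medians "at baseline and at each control visit are compared with either Mann-Whitney U-test or Student's t-test depending on normality of the data distribution". For the blood measures: "Difference in medians of plasma lipid parameters and glucose parameters are analyzed similarly".

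On timing, section 5 says "The first control visit will be after this first period of 12 weeks of exercise", and then "After the first follow-up visit both groups will continue non-supervised exercise for 12 weeks, after which the second control visit will be arranged". The control visits are therefore at weeks 12 and 24, and each man can contribute three measurements.

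On size, section 3 says "The study aims to recruit 40 men on ADT for prostate cancer" and "no power calculation is performed yet". Section 5 says that "the participants are randomized 1:1 to either the supervised or non-supervised exercise group", which gives about 20 men per arm.

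For these outcomes the plan names no analysis set, missing-data method, repeated-measures model or baseline adjustment. Its only adjusted model is the Cox regression for long-term events.

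**The concern.** A two-sample test at week 24 cannot use a man without a week-24 value, even when his baseline and week-12 values are on file. The plan does not say that it restricts the analysis to attenders. That follows by default from the tests it names.

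Outcome-related loss is plausible here. Section 6 implies that men know their group once randomised. During the first 12 weeks one arm attends twice-weekly group sessions while the other trains alone. Section 5 makes continued exercise the special focus of the second control visit, and men who have stopped exercising may be among those who do not return.

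At stake is the effect estimate. Section 3 says that this pilot exists to estimate effect sizes for a larger trial, and a systematic shift would be carried into that design. Separately, and whether or not anyone drops out, unadjusted tests discard the precision that the baseline values offer.

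**Working it through.** The plan gives no drop-out rate, SD, correlation or power figure, so there is no figure of its own to reproduce.

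**Inputs from the documents:** 40 men, 1:1; baseline, week 12 and week 24; a separate two-sample test at each visit.

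**Assumed inputs:** SD 1 and no true effect; correlations 0.6 (baseline–week 12), 0.7 (week 12–week 24) and 0.5 (baseline–week 24); drop-out by week 24 of 10% in the supervised arm and 20% or 30% in the other; logistic drop-out, likelier with a low value, slope 1 or 2 per SD.

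**Step 1: precision.** The standard error of a mean difference in SD units is √(1/n₁ + 1/n₂).
- 20 v 20: √(1/20 + 1/20) = 0.32, 95% half-width 1.96 × 0.316 = 0.62.
- 10% v 30% lost (18 v 14): √(1/18 + 1/14) = 0.36, half-width 1.96 × 0.356 = 0.70.

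**Step 2: week-24 shift** (supervised minus non-supervised, large-sample simulation, simulation error about 0.002). The planned comparison uses attenders only. The likelihood estimate uses all values recorded before drop-out.

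| Drop-out depends on | Rates | Slope | Planned | Likelihood | Removed |
|---|---|---|---|---|---|
| Nothing (random) | either | – | 0.00 | 0.00 | – |
| Recorded week-12 value | 10 v 20% | 1 / 2 | −0.059 / −0.082 | 0.00 / 0.00 | all |
| Recorded week-12 value | 10 v 30% | 1 / 2 | −0.114 / −0.163 | 0.00 / 0.00 | all |
| Unseen week-12 value (lost before week 12) | 10 v 20% | 1 / 2 | −0.059 / −0.083 | −0.037 / −0.054 | 38 / 35% |
| Unseen week-12 value (lost before week 12) | 10 v 30% | 1 / 2 | −0.112 / −0.164 | −0.068 / −0.109 | 39 / 34% |
| Unseen week-24 value | 10 v 20% | 1 / 2 | −0.083 / −0.119 | −0.045 / −0.071 | 45 / 40% |
| Unseen week-24 value | 10 v 30% | 1 / 2 | −0.162 / −0.231 | −0.089 / −0.142 | 45 / 39% |

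At 10% v 30% the shift is 0.11/0.36 ≈ 0.3 to 0.23/0.36 ≈ 0.6 of a standard error.

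**Step 3: wider ranges.** Equal correlations of 0.5, 0.7 or 0.8 between visits, and gaps up to 10% v 40%, were also tried. When drop-out depended on unseen values, the likelihood estimate removed 22–79% of the shift: 22–50% at correlation 0.5 and 60–79% at 0.8. With 20 men per arm, 10% v 30%, slope 1 and no true effect, the planned t-test at nominal 5% rejected 6.0–7.8% of the time.

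**Step 4: rates or selection?** Equal 20% drop-out with the same selection in both arms gave no shift. Equal 20% drop-out with opposite selection gave 0.18–0.29 SD (recorded values) or 0.28–0.32 SD (unseen values). What matters is who leaves each arm, and that also sets the sign.

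**Step 5: baseline adjustment.** With complete data, residual variance falls to 1 − r² of its unadjusted value. For r = 0.5 the fall is 0.25, and for r = 0.7 it is 0.49, so about 25–50%. The likelihood estimate in the simulations left the arms' baseline means free and so did not take this gain: with 20 per arm and 10% v 30%, its SD was 0.33–0.37, against 0.34–0.36 for the planned difference.

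**The case against.** **Nothing shows that drop-out will be unequal or informative.** This is correct. A reader might infer that the planned tests do shift the week-24 result. The documents do not support that: drop-out unrelated to outcome gives no shift, however unequal the rates. The contrast in supervision also exists only in weeks 0–12; afterwards both arms train unsupervised.

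**The model may not cure the problem.** A reader might infer that a longitudinal model would remove most of any shift. That holds only if men leave because of values already recorded. Men who leave because they have stopped exercising since they were last measured are a different case, and men lost before week 12 have only a baseline value. In those settings the table shows 34–45% removed. Some bias remains, though less than under the planned tests.

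**The shift is small beside sampling error.** This is true at 40 men. It is systematic, however, and the estimate is meant to be carried forward.

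**Activity may not be missing.** Monitors are worn throughout the study, so a man who misses the visit may still have activity data after week 12. The special focus in section 5 is also on how many men keep exercising, a proportion rather than the mean simulated here. Both points stand. The concern about missed visits therefore bears more directly on EORTC scores and blood measures.

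**A normal-theory model is less robust than Mann-Whitney at about 20 per arm.** This is fair for bounded EORTC scores and skewed triglycerides, and the fix allows for it.

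**Conclusion.** The point holds as a criticism of the stated method. Per-visit unadjusted tests are available-case by default, and they leave the week-24 difference open to bias if drop-out is related to outcome and differs between arms in rate or in who leaves. On assumed inputs the size is 0.06–0.08 SD at 10% v 20% (0.12 with the strongest selection on an unseen week-24 value) and 0.11–0.23 SD at 10% v 30%, against a standard error near 0.36 SD. If less active men leave mainly from the non-supervised arm, the bias goes against supervision; other patterns reverse it.

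A reader might go on to infer a mis-sized next trial. For example, an assumed true 0.4 SD read as 0.24–0.29 SD would inflate the sample size by (0.4/0.29)² = 1.9 to (0.4/0.24)² = 2.8. The documents support neither the 0.4 SD nor the drop-out behind it, and a 95% half-width of 0.70 SD would move that estimate far more.

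The case for change does not depend on any one drop-out scenario. The model was less biased in every unequal, outcome-related setting examined, and baseline adjustment gains precision even with complete data. This is a recommended change, not an essential one.

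**What to change.** In section 7 (Statistical analysis):

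- State that all randomised men are analysed in their assigned arm.
- For activity, EORTC, lipid and glucose outcomes, replace the per-visit tests with one linear mixed model per outcome: baseline, visit, arm and arm-by-visit, unstructured covariance over weeks 12 and 24, small-sample degrees of freedom. Report the week-12 and week-24 arm differences with 95% confidence intervals.
- Use monitor data after week 12 for men who miss the week-24 visit.
- Log-transform skewed outcomes such as triglycerides, and keep a rank-based analysis as a sensitivity check for bounded EORTC scores.
- Report missing visits by arm, and add a sensitivity analysis that shifts missing week-24 values over a stated range. This should include men lost before week 12, who add nothing to the fit when baseline enters as a covariate.

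The cost is plan wording and modest programming, with no new visits or measurements. The downside is reliance on model assumptions at about 20 men per arm.

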2 STUDY GOALS

[figure not shown]
The study compares effects of supervised and unsupervised exercise on plasma lipid parameters (total cholesterol, LDL, HDL and triglycerides) and glucose levels (fasting plasma glucose, glycated hemoglobin), overall quality of life and on average daily exercise activity in men with prostate cancer and under ADT. As secondary outcome we will study effect on continued exercise activity after the intervention, changes in body composition, blood pressure and risk of fractures, castration resistance as well as death due to prostate cancer and due to any cause.

Study hypothesis is that supervised exercise will improve quality of life, lipid and glucose parameters and increase daily exercise activity more than non-supervised exercise. We also expect higher continued exercise activity, greater changes in body composition and blood pressure and lowered risk of fractures and death in the supervised exercise group.

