Of the secondary outcomes median time to castration resistance and death are compared between the trial arms using Kaplan-Meier analysis and log-rank test. Analysis for risks of castration resistance, death, prostate cancer death, cardiovascular disease, bone fracture and memory impairment will be analysed using Cox regression with months from the study randomization as the time metric. The regression model will be adjusted for the study arm, age at baseline, time between prostate cancer diagnosis and randomization, ADT method and the time on ADT before participating in the trial.

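### Kaplan-Meier medians for time to castration resistance leave prior death unaddressed; read as what patients experience, they would overstate incidence and shorten the time to resistance

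*Combined protocol and SAP*

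**What the plan says.** The long-term follow-up list in section 7 gives the endpoint as "Time from baseline to castration resistance", evidenced by rising PSA or radiological progression. Death is not part of that event. The same list carries prostate cancer death and "Death due to any cause" as outcomes of their own.

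The statistical analysis text in section 7 then states that "median time to castration resistance and death are compared between the trial arms using Kaplan-Meier analysis and log-rank test". The risks of castration resistance, death, prostate cancer death and several diagnoses "will be analysed using Cox regression with months from the study randomization as the time metric".

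Neither part says how a death before castration resistance is handled. The document names no censoring rule, cumulative incidence function, competing-risk model or composite with death. It does not state how long the follow-up through patient files and registries lasts.

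**The concern.** A man who has died cannot later become castration resistant, so death before resistance is a competing event. When death lies outside the event definition, standard Kaplan-Meier treats such a man as censored. It then lets the men still under observation stand in for him, as if he could yet progress. The resulting curve describes a setting in which nobody dies first, and even that reading requires death and resistance to be independent.

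The plan names the median as the quantity to compare, and the median is read off this curve. The trial is a pilot meant to supply effect sizes for a larger study. A median that is too early for real patients could therefore be carried forward as a planning value or quoted as prognosis.

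**Working it through.** **Is there a figure to reproduce?** No. The plan gives no event rate, death rate, median or follow-up length for this endpoint. Every rate below is an assumption, and the calculation shows only direction and plausible size.

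**Inputs from the document**
- Method: Kaplan-Meier medians and log-rank (section 7, statistical analysis).
- Event: resistance only, with death listed separately (section 7, long-term follow-up).
- Sample: "The study aims to recruit 40 men on ADT for prostate cancer" (section 3), and "the participants are randomized 1:1 to either the supervised or non-supervised exercise group" (section 5), so about 20 per arm.

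**Assumed inputs**
- Constant yearly hazard of resistance, h1: 0.10, 0.15 or 0.20.
- Constant yearly hazard of death before resistance, h2: 0.03, 0.05 or 0.08.
- Horizon: 5 years.

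**Formulas, with prior deaths censored**
- Kaplan-Meier incidence at t: 1 − exp(−h1·t). Median: ln 2 / h1.
- Cumulative incidence at t: h1/(h1+h2) × [1 − exp(−(h1+h2)·t)]. Median: −ln[1 − 0.5·(h1+h2)/h1] / (h1+h2).

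The first incidence is never below the second, and the two are equal when h2 = 0. The direction therefore does not depend on the values chosen.

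**Five-year incidence**
- h1 = 0.15, h2 = 0.08. Kaplan-Meier: 1 − exp(−0.75) = 52.8%. Cumulative incidence: (0.15/0.23) × [1 − exp(−1.15)] = 44.6%. Difference: 8.2 points.
- Smallest on the grid, h1 = 0.10, h2 = 0.03: 39.3% against 36.8%, or 2.6 points before rounding.
- Largest on the grid, h1 = 0.20, h2 = 0.08: 63.2% against 53.8%, or 9.4 points.

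**Median at h1 = 0.15**
- Kaplan-Meier: ln 2 / 0.15 = 4.62 years, whatever the value of h2.
- Cumulative incidence, h2 = 0.03: −ln(0.4)/0.18 = 5.09 years.
- Cumulative incidence, h2 = 0.08: −ln(0.2333)/0.23 = 6.33 years.

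**Second set of assumptions.** With a Kaplan-Meier median of 24, 48 or 72 months and prior death of 2%, 5% or 10% per year, the 60-month overstatement runs from 1.9 to 13.6 points. At 48 months and 5% it is 58.0% against 52.1%, with medians of 48.0 and 55.8 months. A simulation of that case with 20 men per arm gave 57.8% against 51.9%, with about 3 prior deaths per arm.

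**Sampling error.** With 20 men and a true incidence of 45%, the standard error is √(0.45 × 0.55 / 20) = 11 points per arm and √2 × 11.1 = 16 points for a difference between arms. This is a binomial approximation with complete 5-year follow-up. The 2.6-9.4 points of the first grid lie below one standard error per arm. The 13.6 points at the extreme of the second set do not.

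**The case against.** **Censoring is inferred.** The plan never says that men who die first are censored. That is right, and the point must be conditional: censoring is what the named method does by default with this event definition. One could also read castration resistance and death as a single composite, for which Kaplan-Meier would be suitable. But section 7 lists them as separate outcomes, and the Cox sentence again names them separately. If a composite is intended, the plan should say so.

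**The comparison between arms.** Section 2 expects "lowered risk of fractures and death in the supervised exercise group", so a reader might infer that the distortion differs by arm and undermines the comparison. The documents do not support that. Suppose supervision halves h2 from 0.08 to 0.04 and leaves h1 at 0.15. Kaplan-Meier then gives 52.8% in both arms, which correctly shows no effect on the hazard of resistance. Cumulative incidence gives 48.4% in the supervised arm against 44.6%, because more of those men live long enough to become resistant. These are answers to two different questions, and the plan does not say that cumulative incidence is its target. The log-rank test and the Cox model stand as cause-specific comparisons.

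**Prostate cancer death.** A reader might extend the point to this outcome. The plan assigns it Cox regression only, so there is no Kaplan-Meier curve to replace.

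**Materiality.** The rates are all assumed, and the shift in the median shrinks to about half a year at the low death rate. ECOG 2 or higher is excluded, which may reduce early deaths, though the document does not quantify this. No primary outcome is touched. All of this stands and limits the importance of the point without removing it.

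**Conclusion.** The point holds as a limited one. The plan compares Kaplan-Meier medians for an event that death can preclude and gives no rule for prior death. If those deaths are censored, as the method does by default, the curve and median overstate the incidence of resistance and shorten the time to it for anyone reading them as patients' experience. The direction is certain whenever some men die first. The size cannot be found from the documents: 2.6-9.4 points at 5 years, and a median of 4.6 years against 5.1 to 6.3, rest on assumed constant hazards. If few men die before resistance, the effect is negligible. On that grid it is smaller than the sampling error of a 40-man pilot. The planned hypothesis tests are not invalidated, and the Kaplan-Meier analysis of all-cause death has no such problem. This is an inexpensive improvement to a long-term outcome and changes no primary conclusion.

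**What to change.** In the statistical analysis text of section 7:
- State how a death before castration resistance is handled.
- Report castration resistance by arm with the Aalen-Johansen cumulative incidence function, with prior death as a competing event.
- Label the log-rank and Cox results for castration resistance as cause-specific hazard comparisons.
- If a Kaplan-Meier median is wanted, use castration-resistance-free survival, with resistance or death as the event. This is a different quantity with an earlier median: at h1 = 0.15 it is ln 2 / 0.18 = 3.9 years for h2 = 0.03 and ln 2 / 0.23 = 3.0 years for h2 = 0.08. It needs its own label.
- Keep Kaplan-Meier for all-cause death.
- Use cumulative incidence for prostate cancer death only if absolute risks are to be reported.

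The cost is a few lines of wording and standard software. Deaths are already followed, so no new data, visits or participants are needed. The downside is one more estimator to report and explain.

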4 INCLUSION- AND EXCLUSION CRITERIA

Inclusion criteria:

- ADT for prostate cancer, regardless of treatment duration
- Willingness to participate in the study; signing of informed consent

Exclusion criteria:

- Unability for physical exertion; ECOG 2 or higher
- High risk for bone fractures as evaluated by the attending clinician
- Non-Finnish speaking; inability to comprehend Finnish

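### The same Cox model with at least five coefficients is planned for six long-term outcomes in 40 men at any event count; Firth penalisation, with a smaller prespecified model at 10 or fewer events, is a cheap, minor improvement

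*Combined protocol and SAP*

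**What the plan says.** The statistical analysis text in section 7 sends six outcomes to Cox regression: "Analysis for risks of castration resistance, death, prostate cancer death, cardiovascular disease, bone fracture and memory impairment". Diabetes is also listed for long-term follow-up but is not in this list, so six is the right count.

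One adjustment set serves all six: "The regression model will be adjusted for the study arm, age at baseline, time between prostate cancer diagnosis and randomization", followed by "ADT method and the time on ADT before participating in the trial". No penalised or exact method is mentioned, so the natural reading is ordinary partial likelihood.

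A second analysis is planned for some of these outcomes: "median time to castration resistance and death are compared between the trial arms using Kaplan-Meier analysis and log-rank test".

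Section 3 sets the size: "The study aims to recruit 40 men on ADT for prostate cancer". It describes a pilot without a power calculation. Section 2 counts "risk of fractures, castration resistance as well as death due to prostate cancer and due to any cause" among the secondary outcomes and expects "lowered risk of fractures and death in the supervised exercise group". No section gives the length of follow-up, the expected number of events, a minimum number of events, or a smaller model for sparse outcomes.

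**The concern.** With few events, a Cox model with many terms has three avoidable weaknesses. The arm log hazard ratio has extra variance, its model standard error tends to be too small, and in some datasets the estimate diverges. The covariate list here does not change with the number of events, so an outcome with 5 events would get the same model as one with 30.

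The hazard ratios for fracture and death address hypotheses stated in section 2. Fracture, cardiovascular disease and memory impairment have no other planned analysis. If a fit fails and no rule exists, the replacement model would be chosen after the data are seen.

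**Working it through.** **Inputs from the documents.** 40 men (section 3), randomised 1:1 (section 5), so 20 per arm. Six outcomes and five model terms (section 7). ADT method has at least two levels, medical and surgical (section 1); its coding is not stated. The plan gives no event count, alpha or target hazard ratio, so it has no figure to reproduce.

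**Coefficients.** Arm 1 + age 1 + time since diagnosis 1 + ADT method at least 1 + time on ADT 1 = at least 5.

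**Events per coefficient (events / 5).** 5/5 = 1; 10/5 = 2; 20/5 = 4. The ceiling is 40/5 = 8, reached only if every man has the event.

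**Simulation assumptions.** Exponential times with censoring at the D-th event; true HR 1 or 0.5; 20% of men in the rarer ADT group; correlation 0.7 between time since diagnosis and time on ADT; covariate log HR 0, 0.3 or 0.6 per SD; 3,000 replicates per cell. Firth's method maximises log L + ½ log|I|, where I is the information matrix. A fit is unusable if |log HR| > 5 or its SE > 5. RMSE = √mean[(estimate − true log HR)²], with unusable fits left out, which favours the planned model at 5 events.

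**Unusable arm estimates at 5 events.** Planned fit: 5–13% at HR 1 and 11–18% at HR 0.5. A smaller run of 400 replicates per cell gave 8–19%. Firth with arm + time on ADT: 0%.

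**RMSE of the arm log HR** (HR 0.5, covariate log HR 0.3; change from planned in brackets):

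| Events | Planned, five terms | Firth, five terms | Firth, arm + time on ADT |
|---|---|---|---|
| 5 | 1.25 | 1.15 (−8%) | 0.94 (−25%) |
| 10 | 0.93 | 0.81 (−13%) | 0.68 (−27%) |
| 15 | 0.68 | 0.63 (−7%) | 0.53 (−22%) |
| 20 | 0.59 | 0.55 (−7%) | 0.48 (−19%) |

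Example: 0.68/0.93 = 0.73, so 27% lower. Smaller runs at 10 events gave 0.93–0.99 for the planned fit and 0.68–0.70 for the reduced one. At 20–40 events, Firth with all five terms lowers RMSE by 2–7%, and type I error is 6–9% with or without it.

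**Sensitivity at 10 events, HR 0.5 (planned vs reduced).** ADT groups split equally: 0.87 vs 0.65. Correlation 0.9: 0.88 vs 0.65. Only age prognostic (log HR 1.0) and omitted from the reduced model: 0.95 vs 0.66. A separate simulation using arm + age as the reduced model agrees: at 10 events the SD fell from 0.78–0.89 to 0.62–0.68.

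**Where to stop reducing.** Power at HR 0.5 with strong covariates (log HR 0.6), planned vs reduced:
- 10 events: 15.4% vs 13.6%, a loss of 1.8 points
- 15 events: 24.2% vs 17.8%, a loss of 6.4 points
- 20 events: 31.3% vs 21.2%, a loss of 10.1 points

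At 15 events the reduced model's mean log HR is also −0.54 against a true −0.69. The reduced model costs little at 10 events and becomes a real trade-off by 15.

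**The case against.** **No conclusion would change.** At 10 events and HR 1, the median SE falls from about 0.73 to 0.65. The ratio of the 95% limits, exp(2 × 1.96 × SE), falls from about 17 to 13, and neither is informative. Schoenfeld's formula (two-sided 5%, assumed) gives 19% power for HR 0.5 at 10 events and 59% at 40; 80% would need 66 events. This stands: most of the imprecision comes from having 40 men.

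**Relevance depends on unstated event counts.** This also stands. With open-ended registry follow-up, some outcomes may pass 20 events, where the gain is slight.

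**Leaving out prognostic covariates pulls the hazard ratio toward 1, and a cut-off makes the adjustment depend on the count.** Both are true, so the reduced model should be confined to very few events. The cut at 10 is a judgement from the power figures, not something in the documents. Firth with all planned terms already prevents most divergence: in the separate simulation with strong covariates, using a slightly different failure criterion, unusable fits at 6 events fell from 4.7–8.5% to 0.6–1.2%. Reducing the model then adds precision (RMSE 0.81 to 0.68 at 10 events).

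**Stronger readings that the documents do not support.**
- A reader might take the five-term SD being 19–45% above an arm-only fit, over 5 to 40 events, as the avoidable loss. Arm-only is not the model proposed here, and most of that excess remains at 20–40 events, where all five terms are kept.
- A reader might infer that prespecified adjustment is itself a mistake. It is a defensible choice; the issue is using the same set at every event count.
- A reader might infer that four outcomes have no analysis besides the Cox model. That is clear for three. For prostate cancer death it is uncertain, because the Kaplan-Meier sentence says death without qualification.
- A reader might infer that the larger trial will be sized on these hazard ratios. No section says so.

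**Conclusion.** The point holds as a minor, inexpensive improvement. The certain part is that at least five coefficients are fitted to each of six outcomes in 40 men, with at most 8 events per coefficient and no rule for sparse outcomes.

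The size depends on assumed event counts, covariate strengths and correlation. The planned arm estimate fails in about 5–19% of fits at 5 events. At 10 events its RMSE is about 0.93, against 0.68–0.70 for the reduced Firth fit. At 20 or more events Firth lowers RMSE by only 2–7%, with no gain in type I error. The change does not make these outcomes adequately powered, and it does not touch the primary outcomes.

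**What to change.** In the Cox regression paragraph of section 7:

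- Fit all six Cox models with Firth penalisation and profile-likelihood 95% confidence intervals, keeping the planned covariates.
- Prespecify that an outcome with 10 or fewer events is modelled with study arm plus one covariate named in advance. Time on ADT is a reasonable candidate, since section 4 admits men on "ADT for prostate cancer, regardless of treatment duration".
- Report the number of events by arm for each outcome.
- Keep the planned Kaplan-Meier and log-rank analyses.

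The cost is analysis wording only: no new data, visits or participants. At 10–20 events, Firth with the planned covariates showed no loss of power. The downside of the reduced model is little adjustment for chance imbalance between arms, and a slight pull of the hazard ratio toward 1 if the omitted covariates are strongly prognostic.
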